#### **5.3.1.2. Probiotics**

Probiotic dietary supplements are prohibited.

### **5.4. Screen Failures**

Screen failures are defined as participants who consent to participate in the clinical study but are not subsequently entered in the study.

Individuals who do not meet the criteria for participation in this study (screen failure) may be rescreened 1 time.

Tests with results that fail eligibility requirements may be repeated once during screening if the investigator believes the result to be in error. Additionally, a participant who fails screening may repeat the screening process 1 time if the investigator believes that there has been a change in eligibility status. Participants who rescreen must reconsent and be assigned a new participant number.

### **5.5. Recruitment Strategy and Retention of Participants**

Specific strategies may be used to recruit and retain under-represented populations in order to improve diversity enrollment. In this clinical study targeting advanced and metastatic gynecological cancers, it is expected that participants may be identified from the local site's database, as well as through referrals. To raise awareness about the clinical study, doctor-to-doctor letters and local flyers may be used, as permitted by each study site and regulatory bodies. Relevant patient advocacy groups may also be contacted.

To enhance participant retention, the sponsor or its designee may use sponsor- and ethics committee-approved visit reminder cards, where permitted by applicable laws. Information regarding study recruitment and retention materials (as allowed by national regulatory requirements in participating countries) will be discussed in the Study Reference Manual.

If appropriate, participants may be reimbursed for eligible out-of-pocket expenses associated with participation in the study. The amount, form, and timing of the reimbursement will be in accordance with applicable laws and the ICF.

## 5.6. Replacement of Participants

In Part 1, participants may be replaced for any of the following reasons:

- Does not meet the eligibility requirements of the study (see Section 7.1.1).
- Withdraws from treatment before the completion of the DLT observation period for any reason other than a DLT (eg, not evaluable for DLT) to ensure a minimum number of evaluable participants.
- Participants who were unable to receive at least  $\geq 75\%$  (ie, 32 doses) of the planned doses of INCB099280 and axitinib during the 21-day DLT observation period and who did not have a DLT will be replaced.

In Part 2, no participants will be replaced.

## 5.7. Data Monitoring Committee

This study will use a DMC to monitor safety and preliminary efficacy once Part 2 has begun. The DMC will make recommendations to the sponsor's clinical team regarding steps to ensure both participant safety and the continued ethical integrity of the study. Also, the DMC may review interim study data, consider the overall risk and benefit to study participants, and recommend if the study should continue in accordance with the Protocol. Specific details regarding composition, responsibilities, and governance of the DMC, including the roles and responsibilities of the various members and the sponsor, executive committee, and protocol team, will be described in the DMC charter. Requirements for and proper documentation of DMC reports, minutes, and recommendations will also be described in the DMC charter, which is reviewed and approved by all DMC members.

## 6. STUDY TREATMENT

Combination treatment with INCB099280 and axitinib will be administered orally BID on a continuous daily dosing schedule (ie, without a break in dosing in the absence of drug-related toxicity). Study treatment will be administered in consecutive 21-day cycles as long as participants are receiving benefit and have not met any criteria for study withdrawal. INCB099280 may be administered for up to 2 years (up to 35 cycles).

If a participant is unable to tolerate combination treatment, they will have met the criterion for study treatment discontinuation. However, on a case-by-case basis, after discussion between the medical monitor and the investigator, a decision may be made to continue INCB099280 monotherapy.

### 6.1. Study Treatments Administered

Study treatment will be dispensed at the visits noted in Table 3. Each participant will be given a dosing diary to record all administered doses, whether the dose was missed or vomited, and any comments regarding missed doses. Compliance with the study treatment will be reviewed at each visit, and the eCRF will then be completed based on the diary.

Details of the study treatment administration are provided in Table 7.

**Table 7: Study Treatment Information**

	Study Treatment 1	Study Treatment 1
Study treatment name	INCB099280	Axitinib
Mechanism of action	PD-L1 inhibitor	VEGFR-1, VEGFR-2, VEGFR-3 inhibitor
Dose formulation	Tablet	
Unit dose strengths/dose levels	■ mg, ■ mg/400 mg BID	1 mg, 3 mg, 5 mg/2 mg BID, 3 mg BID, or 5 mg BID
Route of administration	Oral	
Administration instructions	
Administered as tablets BID every day with a glass of water.
 
INCB099280 may be administered either on an ■ or with a ■.a
 
Note: A ■ (a meal that exceeds ■ calories with ■% calories from fat) is acceptable if consumed at least ■ hours before or after dose administration.
 
Participants must swallow the tablets whole without chewing before swallowing. Tablets must not be crushed, split, or dissolved.
 
INCB099280 and axitinib should be taken in the morning and evening, approximately 12 hours apart. If the administration of either the morning or evening a dose is delayed by more than 4 hours compared with the usual time taken, the dose should be skipped.
 
Participants must be informed that if they miss a dose or vomit after taking the tablets, an additional dose should not be taken. The next dose should be taken at the usual time.
	
Packaging and labeling	
INCB099280 will be provided in a bottle.
 
Each bottle will be labeled as required per country requirement.
	
Axitinib will be provided in a bottle or as a blister pack.
 
Axitinib will be a commercial supply.
 
When applicable, each bottle or blister pack will be labeled as required per country requirement.

Storage	
■-mg tablets: Must be refrigerated.
 
Store at ■
 
■-mg tablets: Store at ■
	Axitinib does not require any special storage conditions.
Status of treatment in participating countries	Investigational	Approved

a An example of a ■ meal in the United States typically contains 11-14 g of fat and a total caloric value of 400-500 kcal (eg, 8 oz of skim [1% fat] milk, 1 boiled egg, and 1 packet flavored instant oatmeal made with water).

## 6.2. Preparation, Handling, and Accountability

The investigator or designee must confirm appropriate temperature conditions have been maintained during transit for all study treatments received and any discrepancies are reported and resolved before use of the study treatment.

Only participants enrolled in the study may receive study treatment, and only authorized site staff may supply or administer study treatment. All study treatment must be stored in a secure, environmentally controlled, and monitored (manual or automated) area in accordance with the labeled storage conditions with access limited to the investigator and authorized site staff.

The investigator or designee is responsible for study treatment accountability, reconciliation, and record maintenance (ie, receipt, reconciliation, and final disposition records). Inventory and accountability records must be maintained and readily available for inspection by the study monitor and are open to inspection at any time by any applicable regulatory authorities. The investigator or designee must maintain records that document the following:

- Delivery of study drugs to the study site.
- Inventory of study drugs at the site.
- Participant use of the study drugs, including tablet counts from each supply dispensed.
- Return of study drugs to the investigator or designee by participants.

The investigational product must be used only in accordance with the Protocol. The investigator will also maintain records adequately documenting that the participants were provided the specified study drug. These records should include dates, quantities, and any available batch or serial numbers or unique code numbers assigned to the investigational product and study participants.

Completed accountability records will be archived by the site. The investigator or designee will be expected to collect and retain all used, unused, and partially used containers of study drug until verified by the study monitor (unless otherwise agreed to by the sponsor). At the conclusion of the study, the investigator or designee will oversee the destruction of any remaining study drug according to institutional SOPs. If, however, local procedures do not allow on-site destruction, shipment of the study drug back to the sponsor is allowed. In this case, the site should (where local procedures allow) maintain the investigational supply until the study monitor inspects the accountability records in order to evaluate compliance and accuracy of accountability by the investigative site. At sites where the study drug is destroyed before monitor inspection, the monitors rely on documentation of destruction per the site SOP.

Further guidance and information for the final disposition of unused study treatments are provided in the Pharmacy Manual.

See [Appendix B](#) for instructions for participant handling of INCB099280. Axitinib should be stored, prepared, and handled according to the nationally approved label.

### **6.3. Measures to Minimize Bias: Randomization and Blinding**

Not applicable.

### **6.4. Study Treatment Compliance**

Compliance with all study-related treatments should be emphasized to the participant by the site personnel, and appropriate steps should be taken to optimize compliance during the study. Compliance with INCB099280 and axitinib will be calculated by the sponsor based on the drug accountability (ie, tablet counts) documented by the site staff and monitored by the sponsor/designee. Participants will be instructed to bring all unused study drugs with them to the study visits in order for site personnel to conduct tablet counts to assess study drug accountability. Returned study drug should not be redispensed to the participants.

Qualified clinical study staff will review the participants' diary entries (see Section 8.1.4) for participant compliance with dose administration instructions. Participants who are noncompliant with their study drug schedule (defined as any missed dose) will have their administration instructions reinforced by the investigator or a qualified designee, and the sponsor should be consulted by the investigator for instruction on the proper handling of participants who are not compliant.

## **6.5. Dose-Limiting Toxicity and Determination of a Recommended Dose for Expansion**

Any AE that is at least possibly related to study treatment and listed in Table 8 will be classified as a DLT. For the purpose of dose finding, decisions on dose will be based on DLTs observed during the first 21 days of treatment.

All DLTs will be assessed for severity by the investigator using CTCAE v5.0. Toxicities with a clear alternative explanation (eg, due to disease progression) or transient ( $\leq 72$  hours) abnormal laboratory values without associated clinically significant signs or symptoms, based on investigator determination, can be deemed a non-DLT. All potential DLTs must be reported to the medical monitor within 24 hours of diagnosis. Participants who receive  $\geq 75\%$  of the doses of INCB099280 and axitinib (ie, 32 doses) at the level assigned or have a DLT will be considered evaluable for determining tolerability of the dose.

Individual participant dose interruptions or axitinib dose reductions may be made based on events observed at any time during treatment; however, for the purposes of dose escalation/de-escalation, expanding a dose level, and determining the MTD for the combination of INCB099280 with axitinib, decisions will be made based on treatment-related events that are observed from the first day of study drug administration through and including the final day of the DLT observation period (Day 21). Although the DLT observation period will be the first 21 days of treatment, DLTs observed beyond this period will be considered in all participants before an RDE is determined. As such, a lower RDE may be selected for further evaluation in Part 2.

### **6.5.1. Definition of a Dose-Limiting Toxicity**

Treatment-emergent AEs listed in Table 8 will be classified as a DLTs.

**Table 8: Definition of Dose-Limiting Toxicity**

Nonhematologic toxicity

 
Any liver function abnormalities that meet the definition of DILI (see Section 9.5).
 
Encephalopathy of any grade.
 
Grade 4 (life-threatening) vomiting or diarrhea.
 
Any Grade <math>\geq 3</math> nonhematologic toxicity EXCEPT the following: 
 
Transient (<math>\leq 72</math> hours) abnormal laboratory values without associated clinically significant signs or symptoms.
 
Nausea, vomiting, and diarrhea adequately controlled with supportive care within 48 hours.
 
An event clearly associated with the underlying disease, disease progression, a concomitant medication, or comorbidity.
 
Asymptomatic changes to lipid profiles.
 
Asymptomatic changes in amylase and lipase (in France only, with abdominal imaging to allow assessment of DLT criteria).
 
Singular or nonfasting elevations in blood glucose (ie, blood glucose excursions will be considered toxicities if fasting blood glucose is elevated on 2 separate occasions).
 
 
 

Hematologic toxicity

 
Grade 3 thrombocytopenia with clinically significant bleeding (ie, requires hospitalization, transfusion of blood products, or other urgent medical intervention).
 
Grade 4 thrombocytopenia.
 
<math>\geq</math> Grade 3 febrile neutropenia (<math>ANC < 1.0 \times 10^9/L</math> and single temperature <math>> 101^\circ F/38.3^\circ C</math> or sustained temperature <math>\geq 100.4^\circ F/38.0^\circ C</math> for more than 1 hour).
 
Grade 4 neutropenia that does not recover to <math>\leq</math> Grade 2 in <math>\leq 7</math> days.
 
Grade 4 anemia not explained by the underlying disease or some other concomitant disorder.
 

Immune-related toxicity

 
<math>\geq 2</math> Grade ocular irAEs.
 
Grade 3 irAEs that do not improve to at least Grade 1 in <math>< 5</math> days with appropriate care or with corticosteroid therapy. Exception: Grade 3 or 4 endocrinopathy that is adequately controlled with hormone supplementation.
 
Grade 4 irAEs, regardless of duration.
 
Grade <math>\geq 2</math> myocarditis and/or pericarditis
 
Grade <math>\geq 2</math> myasthenia gravis, Guillain-Barré syndrome
 
Any grade encephalitis and/or demyelinating disease
 

General

Participant being unable to receive at least 75% (ie, 32 doses) of INCB099280 or axitinib doses during the DLT observation period because of treatment-related toxicity, even if the toxicity does not meet DLT criteria defined above.
 
Note: Exceptions include the DLT exclusions mentioned above.

MTD

 
In Part 1, the MTD will be defined as described in Section 4.1.1 and according to Table 5.
 
In Part 2, participants will be continually evaluated for safety, including AEs <math>\geq</math> Grade 3 that are attributable to the study treatment. If warranted, enrollment of participants may be suspended until the sponsor, investigators, and DMC have determined the appropriate course of action.
 

### 6.5.2. Procedures for Cohort Review and Dose Finding

Decisions on dose will be guided by the hybrid design for dose escalation ([Liao et al 2022](#); see Section 4.1.1) and will be consensus based, involving the investigators and the sponsor. Decision rules, based on the hybrid design after the totality of safety information has been considered, will determine if additional cohorts should involve dose escalation, no change in dose, or dose de-escalation or if a dose level should be eliminated.

Decisions on dose using the hybrid design include the following:

- Decisions will be based on DLTs observed in participants during the first 3 weeks of treatment.
- Enrollment in Dose Level 1 will start with a cohort of at least 3 participants.

Dose de-escalation will proceed if the decision rule to de-escalate to the lower dose level in the dosing algorithm is met, based on the condition that the current dose level was deemed overly toxic. Re-escalation may be considered after at least 3 evaluable participants treated at Dose Level –1 are followed for at least 3 weeks and escalation is warranted.

- Should the decision rule determine "stay," the DLT rate at the current dose level will be used to guide further enrollment.
  - For example, if 2 of 6 participants have a DLT, up to 3 additional DLT-evaluable participants will be enrolled. After the DLT period, if no DLTs occur in the 3 additional participants, an additional cohort of up to 6 DLT-evaluable participants may be enrolled. However, enrollment into that dose level may be stopped if  $\leq 2$  of 11 participants have a DLT because per the decision rule, dose-escalation criteria will have been met.
- If a participant withdraws from study treatment before receiving at least 75% of the planned doses of INCB099280 and axitinib during the 3-week DLT observation period (ie, 32 of the 42 planned doses) for reasons other than study treatment-related toxicity, another participant will be enrolled.

### 6.6. Dose Modifications

The management of some AEs may require dose modifications; these include treatment interruptions (see Section 6.6.1), dose reductions of axitinib (see Section 6.6.2), or the permanent discontinuation of study treatment (see Section 6.6.7).

General guidance on the management of AEs is as follows:

- Every effort should be made to exclude other etiologies in the differential diagnosis (such as neoplastic, infectious, nonspecific inflammatory, metabolic causes) to enable optimal medical management. A specialist referral is strongly encouraged when appropriate.
- When attributing an AE to either INCB099280 or axitinib proves challenging, the most conservative management recommendation should be followed.
  - The investigator's final assessment of causality/attribution and the rationale for this assessment must be documented in the participant's medical records.

- In the event that > 1 AE occurs, dose modifications should be based on the organ system with the greatest degree of toxicity.
- Toxicity management guidelines are provided in [Table 11](#), [Table 12](#), [Table 13](#), and [Table 14](#). If the guidance on the recommended management of a specific toxicity is not covered in this Protocol, participants should be managed according to best clinical practice.
- Supportive care should be provided as clinically indicated and in accordance with local, national, or international guidelines, as appropriate. When prescribing supportive medication, the potential DDIs and known risk QT interval prolongation should be considered (see [Appendix C](#) for further details).
  - The medical management of AEs must be documented in the participant's medical records.
- All dose modifications, including the justification, must be documented in the participant's medical records.

General guidance on the evaluation and management of AEs potentially associated with either INCB099280 or axitinib or both study drugs is as follows:

- Based on the known safety profiles of INCB099280 and axitinib, certain treatment-related AEs are uniquely associated with 1 drug versus the other.
  - For example, hypertension, arterial thrombotic events, proteinuria, and hemorrhagic events are known risks associated with axitinib treatment; irAEs are risks known to be associated with ICI treatment, including INCB099280.
- However, in some circumstances, attributing certain AEs, such as diarrhea, hypothyroidism, and liver enzyme elevation, to INCB099280 may be challenging when overlapping toxicities are expected with axitinib, anticipated for the population under study, or due to effects not related to the study treatment or another condition (eg, infection). In some circumstances, individual case assessment might be clarified with consideration to the following:
  - Time to onset
  - Diagnostic workup: after excluding alternative causes, an irAE should be considered until proven otherwise; events for which irAE-directed therapy was initiated but later stopped in favor of an alternative cause for the event should be captured in the participant's medical records
  - Follow-up response to immunosuppressive therapy
  - Positive dechallenge (eg, if an AE improves/resolves following interruption of axitinib, the event is most likely attributable to axitinib)
  - Rechallenge (if appropriate)

***Regardless of the above, if the AE is severe/life-threatening at the time of onset or rapidly worsens, interrupt both drugs and initiate supportive care.***

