#### **4.1.3. Safety Monitoring**

During the conduct of Part 1 of the study, the sponsor will convene approximately biweekly telephone conferences with the investigative site staff to provide clinical updates on participants who remain on-study. Investigators who are unable to attend and have participants on-study will be requested to provide written updates prior to the meeting to keep all involved parties informed. An agenda will be provided in advance of these meetings, and minutes (including written summaries of cumulative participant-level safety and tolerability information, antitumor activity, and key discussion points and decisions) will be circulated to all investigative sites.

During Part 2 of the study, the sponsor monitoring of the study will include periodic DMC review. If any issues concerning participant safety arise during the study, this will be discussed at the investigator-sponsor meetings and, if appropriate, will be referred to the DMC.

Enrollment of participants into Part 2 may be suspended if > 40% of participants (when 5 or more participants have been enrolled) have an AE  $\geq$  Grade 3 that is attributable to the investigational agent (INCB099280) and that persists over 7 days despite adequate management.

See Section 5.7 for additional information on the Part 2 DMC.

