#### **6.6.6.3. ALT and AST Elevation**

General considerations when evaluating elevated transaminase levels are as follows:

- The determination of immune-related hepatitis mostly relies on the exclusion of other causes, including treatment with axitinib; however, the attribution of AST/ALT elevation to treatment with either INCB099280 or axitinib may be challenging. Potential alternative causes that should also be evaluated and excluded before more definitively concluding the attribution to study treatment include the following:
  - Exposure to other drugs, including over-the-counter and herbal medications that are potentially associated with DILI (eg, statins, acetaminophen)
  - History of alcohol use and recent alcohol use
  - Viral hepatitis A, B, C, and E; cytomegalovirus, Epstein-Barr virus, and other systemic infections

- Autoimmune screening tests
- Liver metastasis and obstructive hepatic disease
- Cardiac or vascular etiology (eg, any cause of severe hypoperfusion of the liver, severe cardiac failure)
- Other causes as appropriate
- Time to onset:
  - Early onset (compared to ICI-related elevations in transaminase levels that occur predominately with the first 6-12 weeks after treatment initiation) suggests the event is likely associated with axitinib after excluding other alternative explanations.
- Response to drug dechallenge:
  - A prompt recovery from elevation in transaminase levels in response to axitinib interruption without confounding by corticosteroid treatment suggests the event is likely associated with axitinib (after excluding other alternative explanations).
  - If the initial elevation in transaminase levels does not respond rapidly to axitinib interruption but responds to subsequent corticosteroid treatment, it suggests a potential for immune-mediated hepatitis by INCB099280. It should be kept in mind that not all cases of immune-mediated hepatitis will respond to corticosteroid treatment.
- A positive rechallenge (see notes below and further details in [Table 14](#); ie, recurrence of elevation in transaminase levels following resumption with study treatment) will provide further support for its attribution.
- Guidelines on causality elevation and management of AST/ALT elevations during axitinib/INCB099280 treatment are described (see [Table 14](#)) for action taken with study medication:

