  - Promptly interrupt (or permanently discontinue) both study drugs and any other suspected concomitant medications, including over-the-counter and herbal medications and supplements.
  - Adequately monitor liver enzymes and LFTs. This should include AST, ALT, alkaline phosphatase, total bilirubin, direct bilirubin, and PT/INR. Repeat LFTs within 24 to 72 hours to confirm the initial laboratory value. Continue to monitor LFTs at least twice weekly, while evaluating other causes, until AST/ALT values are trending downward.

While corticosteroid therapy is essential for managing immune-mediated hepatitis, administering immunosuppressants prior to identifying the most likely causes of transaminase elevation will confound the causality assessment and impact proper management of the event. Initiating corticosteroids should be considered if transaminase elevation:

- Is associated with clinical significant hepatic dysfunction (eg, AST/ALT  $> 3 \times$  ULN with concurrent total bilirubin  $\geq 2 \times$  ULN (excluding biliary obstruction) and/or PT/INR  $\geq 1.5 \times$  ULN
- OR
- Has been persistent or further increased (without an alternative cause identified); consider observing liver biochemistry for approximately 3 to 7 days prior to making the decision if the participant is stable.

Rechallenge after AST/ALT elevation:

- Rechallenge should occur at the discretion of the investigator in consultation with the medical monitor. The guidelines in [Table 14](#) are suggestions; clinical judgment should always be used when deciding whether or not to restart each study drug.

Recommended axitinib dose modifications in case of drug-related toxicity are shown in [Table 12](#), [Table 13](#), and [Table 14](#).

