**Table 13: Management Guidelines for Specific Adverse Events Common to Both INCB099280 and Axitinib**

Event/Severity (CTCAE v5 Grade)	Evaluation and Management
Liver enzyme elevationa	
ALT/AST ≥ 3 × ULN but < 10 × ULN without concurrent total bilirubin ≥ 2 × ULN	
 
Interrupt both INCB099280 and axitinib until resolution to Grade 0-1.
 
Consider rechallenge with INCB099280 and axitinib.
 
 
See Table 14 for further details on event management.

ALT/AST ≥ 3 × ULN with concurrent total bilirubin ≥ 2 × ULN or ALT/AST ≥ 10 × ULN	Permanently discontinue both INCB099280 and axitinib.
Diarrhea	
Grade 1 or Grade 2	Initiate symptomatic medications. See Table 11 for further details on event management.
Grade 3	
 
Interrupt axitinib and initiate symptomatic medications.
 
If diarrhea is controlled, axitinib may be resumed at either the same dose level or reduced by 1 dose level (see Table 9).
 
 
See Table 11 for further details on event management.

Grade 4	Interrupt axitinib until resolution to Grade < 2, then restart axitinib dose reduced by 1 dose level (see Table 9 ). See Table 11 for further details on event management.
Major adverse cardiovascular events	
Grade 3 and Grade 4	Permanently discontinue both INCB099280 and axitinib.

a Consider corticosteroid therapy.

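### The dechallenge criteria in Sections 6.6 and 6.6.6.3 read recovery as pointing to axitinib, but for liver and severe events both drugs are stopped together, so recovery cannot separate them

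*Protocol*

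**What the plan says.** Section 6.6 of the protocol accepts that some events, liver enzyme elevation among them, are hard to assign to one drug, and lists five considerations that may help. One is dechallenge: "Positive dechallenge (eg, if an AE improves/resolves following interruption of axitinib, the event is most likely attributable to axitinib". Section 6.6.6.3 applies the same idea to transaminases: prompt recovery "in response to axitinib interruption without confounding by corticosteroid treatment suggests the event is likely associated with axitinib", once other explanations are excluded.

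The actions prescribed for these events are different from the one the criterion names:

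- Liver enzyme elevation, Section 6.6.6.3: "Promptly interrupt (or permanently discontinue) both study drugs and any other suspected concomitant medications".
- Liver enzyme elevation from 3 to below 10 × ULN without the bilirubin criterion, Table 13: "Interrupt both INCB099280 and axitinib until resolution to Grade 0-1".
- Severe or worsening events, closing line of Section 6.6: "if the AE is severe/life-threatening at the time of onset or rapidly worsens, interrupt both drugs and initiate supportive care".

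Section 6.6.6.3 also says that immune-related hepatitis is established mostly by excluding other causes, and it counts axitinib among those causes. Section 9.3 requires a causality judgment for each drug, and Section 10.4.2.1 tabulates irAEs.

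**The concern.** Dechallenge is informative about one of two drugs only if the other is held constant. The two criteria omit that condition, and the protocol's own instructions remove it for liver enzyme elevation and for severe or rapidly worsening events. As worded, any event that resolves after both drugs are stopped also resolves after axitinib is stopped, so it satisfies the criterion whichever drug caused it.

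The lean is one-sided. No mirror criterion credits recovery after INCB099280 interruption to INCB099280. Because a diagnosis of immune-related hepatitis depends on first excluding axitinib, an uninformative recovery read as an axitinib effect can also remove the event from the irAE table. What is at stake is the recorded rate of INCB099280-related and immune-related liver events for the investigational drug.

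**Working it through.** The plan states no figure on this point, so none can be reproduced. The check sets the passages side by side.

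**1. What recovery shows under each action.** Assume an event resolves when its cause is withdrawn.

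| Action | Axitinib is the cause | INCB099280 is the cause |
|---|---|---|
| Axitinib stopped, INCB099280 continued | recovers | does not recover |
| Both stopped | recovers | recovers |

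In the first row, recovery points to axitinib. In the second row it is expected either way, so it carries no weight for one drug over the other. The criteria in Sections 6.6 and 6.6.6.3 do not distinguish the rows.

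**2. Which row applies.** Section 6.6.1 lets the drugs be interrupted independently, and Table 12 has many axitinib-only interruptions. The first row therefore occurs, and the criterion works there. Liver enzyme elevation (Section 6.6.6.3, Table 13) and severe or rapidly worsening events (Section 6.6) fall in the second row.

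**3. How the liver criterion can be met in the second row.** Section 6.6.6.3 suggests watching liver tests for about 3 to 7 days before deciding on steroids in a stable participant whose elevation persists or rises. Recovery in that window, with both drugs off, is prompt and free of steroid confounding. Once other explanations are excluded, it meets the wording that points to axitinib.

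**4. Whether a later step separates the drugs.** Table 14:

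| Scenario | ALT/AST | Rechallenge |
|---|---|---|
| 1 | > 3 × ULN with hepatic dysfunction | none |
| 2 | > 3–5 × ULN, no dysfunction | sequential, axitinib first for 2–3 weeks |
| 3 | > 5 to 10 × ULN, no dysfunction | none |
| 4 | > 10 × ULN, no dysfunction | none |

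Table 14 labels > 3–5 × ULN as Grade 2 and > 5 × ULN as Grade 3 or 4. Under that table, Grade 3 or 4 liver events never receive a separating rechallenge. Table 13 lets rechallenge be considered up to 10 × ULN, which does not agree with Scenario 3. Those two tables need reconciling on their own account, and this step follows Table 14, to which Table 13 refers.

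**5. Which outputs depend on the split between drugs.**

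- Dependent: per-drug causality (Section 9.3), irAE tabulation (Section 10.4.2.1) and the Part 2 suspension trigger (Section 4.1.3).
- Not dependent: DLTs (Section 6.5), TEAE incidence and treatment-related summaries (Section 10.4.2.1). These count relation to study treatment as a whole.

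**6. Rough number of ambiguous events (assumption).** Section 2.3.2 reports ALT increased in 26.8% of participants (Grade 3 or 4 in 13.3%) with axitinib plus pembrolizumab in renal cell carcinoma. Carried over to 120 Part 2 participants, this gives 0.268 × 120 ≈ 32 of any grade and 0.133 × 120 ≈ 16 of Grade 3 or 4. These are events that might pose the question, not events misattributed. The drug and the disease differ, and not every ALT increase reaches 3 × ULN. The number shifted could be anywhere from none to all of those truly due to INCB099280.

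**The case against.** The strongest reply is that Section 6.6 is not a classification rule. Dechallenge is one optional aid among five, offered as an example and hedged. The same list says that, after alternatives are excluded, "an irAE should be considered until proven otherwise", which pulls towards INCB099280. Time to onset and steroid response are weighed too: slow recovery that then responds to steroids points to immune-mediated hepatitis. Speed of recovery may itself carry some information. The investigator makes and documents the final attribution, and both drugs may be suspected.

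Most of this stands. A reader might infer that INCB099280 toxicity will be systematically booked to axitinib; with these counterweights in the text, the documents do not support that. They do not remove the gap, however. The dechallenge sentence, read literally, is one way to prove otherwise. No recovery time is given that would separate the drugs. Section 9.3 asks for positive evidence of a relationship and not merely that one cannot be ruled out, and here the text supplies such evidence for axitinib only.

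A second tempting inference is that misattribution could keep Part 2 below its suspension trigger, which counts Grade 3 or higher AEs "that is attributable to the investigational agent (INCB099280") in more than 40% of participants. The arithmetic can be made to look large. With 20 participants the trigger needs 9 (9/20 = 45%). With X ~ Binomial(20, p(1 − m)) and p = 50%, P(X ≥ 9) falls from 74.8% at m = 0 to 58.6% at m = 10% and 31.7% at m = 25%, where m is an assumed share credited to axitinib alone. But the trigger also requires the event to last more than 7 days despite management, and events that recover promptly would often not count whichever drug is named. Section 4.1.3 does not state a per-cohort count, suspension is discretionary, and Table 8 separately allows suspension for events attributable to study treatment as a whole. These percentages are therefore not the size of the effect.

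**Conclusion.** The point holds as a defect of attribution wording. Where the protocol stops both drugs together, recovery does not discriminate between them, yet Sections 6.6 and 6.6.6.3 read it as favouring axitinib. The consequence is a risk of under-recording INCB099280-related and immune-related liver events. The risk is least correctable above 5 × ULN, where Table 14 allows no rechallenge.

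Its size cannot be derived from the documents, because the share of events that would be misread is not given. DLT decisions and overall treatment-related summaries are untouched, and any effect on the suspension trigger is likely small. The conclusion assumes that investigators apply the dechallenge wording literally after a joint stop and that Table 14 is followed, although Section 6.6.6.3 calls its guidance suggestions. The change should be made because it is cheap and removes a directional lean from a safety result for the investigational drug.

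**What to change.** Add two sentences to the dechallenge bullet in Section 6.6 and to the matching bullet in Section 6.6.6.3:

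1. Positive dechallenge supports attribution to axitinib alone only when INCB099280 was continued during the axitinib interruption.
2. Recovery after both drugs were interrupted together does not discriminate between them and is not by itself grounds to exclude INCB099280 or an irAE.

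Leave the per-drug causality judgment to Section 9.3. A default of recording such events as suspected for both drugs should not be added, because it would conflict with that section's meaning of a reasonable possibility. No interruption or rechallenge rule changes.

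The cost is the added text and a matching note in the eCRF guidelines. The downside is that some axitinib-caused events may also be recorded as INCB099280-related, making that rate slightly less favourable.
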